Risk minimization, management, and assessment procedures have been implemented in the study to minimize and assess potential risks to participants who participate in this clinical study with gabapentin. Components include: (1) specific study eligibility and exclusion criteria to ensure that participants who have underlying characteristics that potentially increase their risk for an adverse outcome are excluded. These include patients with a history of previous sensitivity to gabapentin. (2) Protocol-specific procedures for minimizing and managing AEs: sedation is the most common AE to gabapentin, and we will address this by titrating upwards on the dose every 3rd day, and always increasing the nighttime dose first; (3) overview surveillance by the independent Data Safety Monitoring Board; (4) ongoing follow-up throughout the study by research personnel twice weekly, coinciding with dose increases to check for AE as shown in the table below.

Refer to the TEVA-Gabapentin (gabapentin) TEVA Canada Product Monograph (DIN 02244515) for a detailed description of warnings, precautions, and adverse events: https://health-products.canada.ca/dpd-bdpp/info.do?lang=en&code=68492

The following potential side effects occurred in clinical trials across ages 3-adults at rates higher than in placebo groups:

- Somnolence
- Dizziness
- Fatigue
- Nausea and/or Vomiting
- Increase Weight
- Emotional Lability
- Hostility
- Hyperkinesia
- Respiratory Infection
- Fever
- Swelling of limbs
- Gait disturbance

Implementation and adherence

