The risk of serious side effects of respiratory depression with concomitant use with opioids is acknowledged (BC Children's Hospital Integrated Pain Service Gabapentin Information http://www.bcchildrens.ca/Pain-Services-Site/Docu-Sheet. Accessed at: ments/BCCH1455Gabapentin.pdf. Retrieved on October 4, 2020). A minority of patients might be on opioids. Dose adjustments will be added when gabapentin is used with a concomitant opioid or other CNS depressant medication: the family will be advised to return to the previous stable, safe dose in the protocol, and the subject will remain at that dose with no further escalation for the duration of the trial arm. This schedule will be duplicated on the parallel arm (active drug or placebo) to maintain masking. The participants are highly monitored, often with continuous oxygen saturation monitoring and/or "baby-cam" devices observing them during sleep. During the daytime they are with family, or professional caregivers (aides, nurses, etc.). These individuals will be advised to watch for respiratory depression and sedation that occur well before fatal apnea, and how to respond.

While there are no prohibitions on concomitant care, any care or medications unrelated to the trial will be noted in the CRFs for each participant.

Participants are sometimes obtaining respite care at facilities with nursing and physician care. Medical reconciliation is done at each admission. Parents will be provided with a letter to share with these programs outlining the study, the drug being tested, and a 24-hour pager to contact for further information or concerns

Active Participants < 15kg in mg per kg

Day	Morning mg/kg	Noon mg/kg	Evening mg/kg	Total mg/kg per day	% Change
1*	0	0	5	5	0
2	0	5	5	10	100%
3	5	5	5	15	50%
4	5	5	5	15	0%
5	5	5	10	20	33%
6	5	5	10	20	0%
7	5	5	10	20	0%
8	10	10	10	30	50%
9	10	10	10	30	0%
10	10	10	10	30	0%
11	13.3	13.3	13.3	40	33%
12	13.3	13.3	13.3	40	0%
13	13.3	13.3	13.3	40	0%
14	17	17	17	50	25%
15	17	17	17	50	0%
16	17	17	17	50	0%
17	20	20	20	60	20%
18	20	20	20	60	0%
19	20	20	20	60	0%
20	13.3	13.3	13.3	40	-33%
21	6.7	6.7	6.7	20	-50%
22	0	5	5	10	-50%
23	0	0	5	5	-50%
24	0	0	0	0	-100%
25	0	0	0	0	0%
Switch over*	-	-	-	-	-

^{*}Day one or 26 if switching over, not both.

Active Participants > = 15kg in mg per day

Day	Morning mg	Noon mg	Evening mg	Total mg/kg per day	Total mg/day	% Change
1*	0	0	75	5	75	0
2	0	75	75	10	150	100%
3	75	75	75	15	225	50%
4	75	75	75	15	225	0%
5	100	100	100	20	300	33%

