3.11. Data Monitoring

Formal Committee

The Gabapentin Trial will be monitored by a Data Safety Monitoring Board (DSMB), nestled under the Research Network CHILD-BRIGHT, sponsoring this trial. The DSMB will review the reports created by the study team on a bi-annual basis. Based on review of the reports, the DSMB may consider making recommendations on the adverse events, protocol deviations and ongoing monitoring of the data as assembled. The duties, activities and referential framework for the DSMP will be laid out in the Data Safety Monitoring Plan.

Monitoring

The study site agrees to allow the Sponsor-Investigator's monitor(s) direct access to the study records and medical records from those patients enrolled in the clinical study as well as drug accountability records. Monitoring for this study will consist of data management review focused on erroneous data, illogical entries, and missing data, and on central monitoring of clinical and operational data reviewed for outliers and trends. On-site monitoring will be targeted based on the results of data management and of central monitoring reviews. A site initiation, with the presence of the site monitor, will ensure that best Good Documentation Practices (GDP) are set up. A site visit when half of the participants have been enrolled and at study close out will follow the site initiation and ensure that GDP is being followed and that reporting on protocol deviations or adverse events during the trial has been done when necessary.

Plans for Site Monitoring are laid out in the Data Safety Monitoring Plan.

Early Termination of the Trial

As part of their duties to ensure that research participants are protected, the institutional REB or other government organizations may discontinue the study at any time. Regulatory authorities and the Sponsor-Investigator retain the authority to suspend additional enrollment for the entire study as applicable.

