Probably Related: There is evidence to suggest a causal relationship, and the influence of other factors is unlikely. The clinical event, including an abnormal laboratory test result, occurs within a reasonable time sequence to administration of the drug, is unlikely to be attributed to concurrent disease or other drugs or chemicals, and follows a clinically reasonable response on withdrawal (de-challenge). Re-challenge information is not required to fulfill this definition.

Possibly Related: There is some evidence to suggest a causal relationship (e.g., the event occurred within a reasonable time after administration of the trial medication). However, the influence of other factors may have contributed to the event (e.g., the participant's clinical condition, other concomitant events). Although an adverse drug event may rate only as "possibly related" soon after discovery, it can be flagged as requiring more information and later be upgraded to "probably related" or "definitely related", as appropriate.

Unlikely: A clinical event, including an abnormal laboratory test result, whose temporal relationship to drug administration makes a causal relationship improbable (e.g., the event did not occur within a reasonable time after administration of the trial medication) and in which other drugs or chemicals or underlying disease provides plausible explanations (e.g., the participant's clinical condition, other concomitant treatments).

Not related: The AE is completely independent of study drug administration, and/or evidence exists that the event is definitely related to another etiology. There must be an alternative, definitive etiology documented by the clinician.

Intensity

The Intensity (severity) for each AE (including SAE) will be graded according to the RN or MD who examines and evaluates the participant, given the clinical team's experience with severely disabled children, as mild, moderate or severe and potentially life-threatening.

Reporting

Only SAEs that meet the definition of an unanticipated problem (i.e. unexpected, related and involving greater risk) are required to be reported to the DSMB, the institutional REB and Health Canada. Expected, unrelated and/or non-serious adverse events will not be reported to the DSMB and the institutional REB. Reportable SAEs will be reported within 24 hours of the site becoming aware of the event

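### As written, section 3.12 keeps serious adverse events that are classed as expected or judged unrelated from the DSMB, in conflict with the DSMB's role in sections 3.3 and 3.11

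*Protocol*

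**What the plan says.** Protocol section 3.12, under Reporting, opens with what must be sent to the DSMB, the ethics board and Health Canada: "Only SAEs that meet the definition of an unanticipated problem (i.e. unexpected, related and involving greater risk) are required to be reported". The next sentence states the converse for the DSMB and the ethics board: "Expected, unrelated and/or non-serious adverse events will not be reported to the DSMB and the institutional REB". A third sentence gives a 24-hour limit for reportable serious events.

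Two other sections describe what the DSMB is for. Section 3.3 (Gabapentin Risks and Precautions) lists the components that protect participants, and one of them is "overview surveillance by the independent Data Safety Monitoring Board". Section 3.11 (Formal Committee) says: "The DSMB will review the reports created by the study team on a bi-annual basis". On the strength of those reports, "the DSMB may consider making recommendations on the adverse events, protocol deviations and ongoing monitoring of the data as assembled". Section 3.11 leaves the detail to a Data Safety Monitoring Plan, which is not among the documents at hand.

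Three further provisions bear on the point:
- Section 3.12 (Relationship to Treatment) has the clinician who examines the participant decide causality.
- Section 3.12 also has the Study Medical Monitor notified of clinically significant adverse events.
- Section 4.2 has minor deviations from the dosing sequence reported to the DSMB. Its example is a slower titration because of minor side effects.

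**The concern.** The sentence in 3.12 excludes events by category and carries no time limit. Because it joins its attributes with and/or, any one of them is enough for exclusion, and seriousness does not override the other two. A hospitalization or a death could therefore stay out of the DSMB's sight if it is classed as expected or judged unrelated.

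That sits badly with a board relied on for surveillance and asked for recommendations on adverse events. With a marketed drug, most foreseeable harm is of a known kind, and 3.12 itself anticipates that clinically significant events will mostly be known side effects of gabapentin. These children also have complex illness, so an alternative cause for an event is often available and the relatedness judgement is open to error. At stake is whether the board can see individual serious events irrespective of the site's classification, and whether it can see known effects accumulate.

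**Working it through.** No arithmetic underlies the rule. The check is to apply the two reporting sentences in 3.12 to each kind of serious event and compare the result with what 3.3 and 3.11 need.

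**Step 1. Inputs.**
- Inclusion rule (3.12): serious, unexpected, related and of greater risk, all four together.
- Exclusion rule (3.12): expected, unrelated or non-serious, any one sufficient.

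**Step 2. Apply both rules to serious events.**

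| Expectedness | Relatedness | Goes to the DSMB under 3.12? |
|---|---|---|
| Expected | Related | No |
| Expected | Unrelated | No |
| Unexpected | Unrelated | No |
| Unexpected | Related | Yes, if it also involves greater risk |

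Two levels of expectedness times two of relatedness give 2 × 2 = 4 combinations. Three are excluded and the fourth is conditional. This counts categories and does not predict how many events fall in each. Non-serious events are all excluded.

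**Step 3. Compare with the DSMB's stated task.** Section 3.11 has the board recommend on adverse events after reviewing reports from the study team, but does not say what adverse-event content those reports carry. If the exclusion in 3.12 governs them, they hold at most the fourth row of the table. The surveillance relied on in 3.3 would then cover neither known effects nor events attributed to other causes.

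**Step 4. Look for another route to the DSMB.**
- The Medical Monitor route in 3.12 handles single cases with the Investigator. The section does not say that these are forwarded to the DSMB.
- The provision in 3.12 on suspected unexpected serious adverse reactions names investigators, institutions, ethics boards and Health Canada. It does not name the DSMB, and it covers only unexpected reactions.
- Section 4.2 sends dosing deviations to the DSMB. The board may learn of a side effect as the reason for a deviation, but an event that leads to no deviation does not arrive this way.

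None of these restores all serious events or cumulative counts to the board.

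**Step 5. Number of opportunities.** The trial summary gives a total duration of 12 months. Taking bi-annual to mean every 6 months, 12 / 6 = 2, so about two scheduled reviews are expected. With so few, the content of each report matters.

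**The case against.** The strongest reply is that the sentence concerns expedited notification only. It stands under Reporting, follows a statement of what is required to be reported, and is followed by a 24-hour limit. Section 3.11 would then be a separate, periodic channel, and asking the board to advise on adverse events presupposes that its reports contain some. On that reading the protocol lacks one qualifying word. This is plausible and may be what was meant. It does not remove the point, because the 24-hour limit is attached to reportable events only and the exclusion itself is unqualified.

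A second reply is that the Data Safety Monitoring Plan sets the content of the reports. It may. But the difficulty is a rule that the protocol does state, and a subordinate plan that supplied these events to the DSMB would depart from that rule.

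A third reply is that with 10 participants a comparison of event counts between treatments will seldom be informative. That is fair, and it makes the listing of individual serious events the more valuable part of the fix.

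Three stronger readings are tempting, and the protocol does not support them:
- A reader might infer that serious respiratory depression would be withheld, since 3.3 (Concomitant Care) says: "The risk of serious side effects of respiratory depression with concomitant use with opioids is acknowledged". The protocol never classes it as expected for reporting purposes, and it is not in the side-effect list in 3.3.
- A reader might infer that all 12 side effects in that list are expected by definition, so that none could reach the DSMB. The protocol does not define expected. Its nearest cue, in 3.12, is documentation in the Product Monographs, and it does not say how an unusually severe form of a known effect would be classed. Section 4.2 also lets some side effects reach the board through deviations.
- A reader might infer that a mistaken judgement of unrelated is never reviewed. Clinically significant events go to the Medical Monitor, and follow-up of an unresolved event ends only when the investigator and the Medical Monitor agree.

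**Conclusion.** The concern holds as a conflict within the protocol. Section 3.12, read as written, excludes three of the four kinds of serious event from the DSMB and makes the fourth conditional, while sections 3.3 and 3.11 rely on the board to oversee and advise on adverse events. The deficit is limited to the DSMB's view of serious events and cumulative adverse events. Recording, follow-up and case-level review by the Medical Monitor remain in place.

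The conclusion rests on taking the exclusion literally. If it was meant for expedited reports only, the fault is one of wording, and the same correction settles it. The content of the Data Safety Monitoring Plan is unknown. The point should be corrected, but it does not affect the efficacy analysis.

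**What to change.** Reconcile sections 3.3, 3.11 and 3.12 in two places:

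1. In 3.12 (Reporting), limit the exclusion to expedited, 24-hour reporting, so that it no longer governs the periodic DSMB reports.
2. In 3.11 (Formal Committee), state that each bi-annual report lists every serious adverse event, whatever its expectedness or judged relatedness, and tabulates cumulative adverse events by masked treatment (coded labels, with the allocation not disclosed).

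The Data Safety Monitoring Plan should then be checked against the revised wording. The cost is a small text change and one table in reports already planned. The protocol already requires all adverse events to be recorded, so no new data collection is needed.

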4. ETHICS AND DISSEMINATION

4.1. Research Ethics Approval

The UBC Research Ethics Board (REB) will review the protocol and all appropriate study documentation to safeguard the rights, safety, and well-being of the participants. The study will be conducted only when and where ethics approval has been obtained. A copy of the protocol (including protocol amendments), all versions of informed consent forms, other information to be completed by participants such as survey instruments or questionnaires, and any proposed advertising/recruitment materials must be reviewed and approved by the UBC REB prior to implementation of the trial. The investigator will be responsible for obtaining REB approval of the annual Continuing Review and any protocol modifications throughout the duration of the study.

This study will be conducted in accordance with the guidelines of the University of British Columbia Research Ethics Board and the principles in the Tri-Council Statement on research conduct. The Investigators will be thoroughly familiar with the appropriate use of the study treatment as described in the protocol and the Teva-Gabapentin Product Monograph.

4.2. Protocol Deviations

Minor deviations from the drug sequence (see Dosing Schedule) will be permitted without the prior written approval of the REB if, in the Investigator's opinion, it is required to enable a participant to continue in the trial. An example would be extending the time between dose titration increases if the subject (parent/caregiver) believes it would improve minor side effects. Parallel adjustments would be made in the gabapentin and placebo sequences to preserve blinding. These deviations will be reported to the Data Safety Monitoring Board (DSMB).

Major deviations in the study protocol will not occur without REB approval except when the modification is needed to eliminate an immediate hazard or hazards to participants. Any deviations that may affect a participant's informed consent, especially those increasing potential risks, must receive prior approval from the REB unless performed to remove an immediate safety risk to the participants. In this case it will be reported to the REB, and the DSMB immediately thereafter. Any departures from the protocol must be documented.

4.3. Informed Consent Process

All participants will be given detailed oral and written information about the study prior to enrollment. A Consent Form describing in detail the study medication and study procedures and risks will be given to each participant (caregiver). Each participant will have sufficient opportunity to

discuss the study, have all of their questions addressed and consider the information in the Consent Form prior to agreeing to participate in the trial. Participants must sign the Consent Form prior to any study procedures being done specifically for the trial. Participants may withdraw consent at any time during the course of the study without prejudice. The Consent Form will be signed and dated by the participant and the person obtaining consent, from the study team. The original signed informed consent form will be retained in the participant's study files and a copy will be provided to the participant.

4.4. Confidentiality

All participant-related information including Case Report Forms, evaluation forms, reports, clinical notes etc. will be kept strictly confidential. All records will be kept in a secure, locked location and only accessible to research staff. Participants will be identified only by means of a coded number specific to each participant. All computerized databases will identify participants by numeric codes only and will be password protected.

4.5. Access to Data

Upon request, and in the presence of the investigator or his representative, participant records will be made available to the study sponsor, monitoring groups representative of the study sponsor, representatives of funding groups, and applicable regulatory agencies for the purpose of verification of clinical trial procedures and/or data, as is permissible by local regulations.

4.6. Ancillary and Post-Trial Care

Participants may have access to gabapentin after completing the study through their primary healthcare provider.

6. APPENDICES

6.1. List of Appendices

Table 1 Dosing Schedule

Table 2 Participant Timeline

Table 3 Schedule of Events

Table 4 Medication and Placebo Assessments

Appendix 1 Eligibility Assessment

Appendix 2 Consent Form

Appendix 3 Demographic Information

Appendix 4 Health Information Form

Appendix 5 Pain Survey

Appendix 6 Health Update

Appendix 7 NCCPC-R

Appendix 8 PROMIS-57

Appendix 9 Participant Questionnaire

Appendix 9b Pre-Participation Questionnaire

Appendix 10 Adverse Events Log

Appendix 11 Concomitant Medications

[figure not shown]
6.2. Schedule of Enrolment, Interventions, and Assessments

Gabapentin Trial Diagrams and Summaries

Table 3 shows which assessments happen during specific phases of the trial. Table 4 shows the exact timepoint assessments are administer

Trial Design Summary

- Repeated Measures Single Cross-Over Trial (Treatment and Placebo)
- We will recruit 10 study participants. These participants will have completed the PIUO Pathway without resolution of pain. They will have severe neurological impairment and unexplained, untreated pain.
- The study participants will be randomized to treatment or placebo arms. This first session will take 25 days. During this time the treatment arm gabapentin dose will be slowly increased until an effective dose or maximum dose (60mg/kg/day) is reached, whichever comes first.
- The participants will then undergo a three-day long washout period, where neither drug nor placebo will be administered.
- Following this, the participants that were on placebo previously will switch to gabapentin treatment and those who were on gabapentin treatment will switch to placebo. This will again go on for 25 days, with the gabapentin dose increasing throughout.
- NCCPC-R, PROMIS-57 and Pain Surveys will be administered throughout the trial to obtain data
- The total participant time will be around 55 days.
- The diagram below depicts the Gabapentin trial design.

N-of-1 Design

The Gabapentin Trial will use an N-of-1 design. This means that each participant will be his or her own experiment, acting as both treatment and placebo participants. In an N-of-1 trial, each participant's treatment data is compared to his or her own placebo data, and the results are specific to

the individual participant. A small "N" such as 10 (as we are going to recruit for the Gabapentin Trial) can provide an adequate amount of data when using an N-of-1 design because 10 separate data sets and results will be produced. Multiple N-of-1 trials that are conducted on similar patients taking similar drugs can be amalgamated to give broader results.

N-of-1 trials allow for the development of personalized medicine, which is ideal when working with a population of high heterogeneity, such as children with severe neurological impairment. Each of the participants will be unique in his or her own physical and emotional health needs. An N-of-1 trial allows the researcher to determine if treatment is effective in a specific individual, as well as the optimal dose, tolerability and potential side effects of the treatment for that individual. A standard cross-over trial may elicit the answer to the question of "Does drug X relieve pain in children with severe neurological impairment?" but an N-of-1 trial can answer the question of "Does 10mg/kg of drug X relieve pain in a 10-year-old female whose severe neurological impairment is caused by Rett Syndrome?".

The diagram below depicts a sample N-of-1 trial with five participants. Each colour represents an individual participant, and their cause of severe neurological impairment is listed on the right. Each participant will trial the treatment (in our case Gabapentin) and the placebo, in randomized order. The results (check mark = pain resolved and "X" = pain not resolved) are also coloured in to show that the results are specific to the individual. For example, the treatment that worked for the participant with Rett Syndrome may have been 30 mg/kg/day of drug X, while the effective treatment for the participant with cerebral palsy may have been 15mg/kg twice a day, because he/she was overly sensitive to the sedative effects of drug X and required a lower dose.

[figure not shown]

Table 3: Gabapentin Trial Events Schedule

Study Phase	Screening and Enrollment	Baseline Visit	Sequence 1	Study Visit	Sequence 2	Study End	Follow Up
Study Time Point	- 4 to 0 weeks	Day 1 of Period 1	Day 1 – 26 of Period 1	Day 1 of Period 2	Day 1 – 26 of Period 2	Day 26 of Period 2	1 week post Study End
Eligibility Assessment	X						
Informed Consent	X						
Demographic Information		X*					
Health Information Form		X*					
Medical History		X*					
Physical Exam		X*					
Pre-Participation Questionnaire		X					
Randomization		X					
Study Drug Dispensing		X		X			
Pain Survey			X		X	X	
NCCPC-R			X		X	X	
PROMIS-57			X		X	X	
Adverse Events Log			X		X	X	

Version 3.0 October 4, 2020 Page 38 of 45

Health Update		X		X	X	
Concomitant Medications		X		X	X	
Study Drug Accountability			X		X	
Participation Questionnaire						X

^{*}If the child participated in the PIUO Study within the last 6 months these items will already be completed and only a Health Update is necessary to complete prior to drug dispensing. If the child did not participate in the PIUO Study all items will be completed and the PIUO Pathway will be implemented prior to drug dispensing. If a treatable cause for the child's PIUO is uncovered, the child will be withdrawn from the gabapentin trial.

Version 3.0 October 4, 2020 Page 39 of 45

 Table 4: Medication and Placebo Assessment Schedule for all subjects

Day	Health Update	Concomitant Medications	NCCPC-R	Pain Survey	PROMIS-57
1	X	X	X	X	X
2					
3					
4					
5			X	X	
6					
7					
8			X		
9					
10					
11	X		X		
12			X	X	X
13			X		
14			X		
15			X		
16			X	X	X
17			X		
18			X		

Version 3.0 October 4, 2020 Page 40 of 45

19			X	X	X
20					
21					
22			X		
23					
24					
25					
Switch Over*	X	X	X	X	X

^{*}Day 1 or 26 if switching over, not both

Version 3.0 October 4, 2020 Page 41 of 45

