1. TRIAL SUMMARY

Title	Efficacy of Gabapentin in Treating Pain in Children with Severe Neurological Impairment
Brief title	Gabapentin Trial
Primary registry and trial number	2020GabTrial
Secondary identifying numbers	Clinical Trials.gov: NCT03464773 SCA-145104 RI MUHC Ref# 7733
Sources of monetary or material support	Canadian Institutes of Health Research (CIHR) SPOR Networks in Chronic Disease, CHILD-BRIGHT
Primary sponsor	[name]
Study officials/Investigators	[name], [name], [name], [name]
Central contact	[name]
Number of centers	1
Primary objective	Evaluate the effectiveness of gabapentin to decrease pain and irritability in children with SNI, when source of pain and irritability is attributed to neurological dysregulation and not to a nociceptive-inflammatory cause
Secondary objective	 Identify the optimal dosing of gabapentin in reducing pain and irritability Identify the latency time for gabapentin to show effectiveness Evaluate the safety and tolerability of gabapentin
Exploratory objective	Evaluate whether parent/caregiver stress and function improve if gabapentin reduces child's pain and irritability
Interventions	Participants will receive liquid gabapentin, compounded from Teva-Gabapentin (gabapentin) 400 mg capsules (DIN 02244515). cf. below

Key eligibility criteria	Children 3 to 18 years old with severe neurological impairment who are experiencing pain and/or irritability of unknown origin (PIUO)
Study design	Repeat measures single cross-over trial (treatment and placebo)
Randomization	Computer-generated, simple randomization (starting with treatment or placebo). Each participant serves as their own control.
Target sample size	10
Study duration	Total study duration 12 months, participant study duration 4 months
Medication administration and dosing	Gabapentin capsules will be compounded with flavourings to create a 100 mg/mL oral solution. The starting dose will be 5 mg/kg/day as oral liquid or via g-, j-tube. The dose will be escalated as described in Section 6.2. The maximum dose is 60 mg/kg/day in participants < 15 kg, or 45 mg/kg/day (675 mg) in participants > 15 kg.
Primary outcomes	The pain and irritability score on the NCCPC-R through days 11-19 on active drug compared to placebo. An 11-point decrement in the NCCPC-R score with no rebound x 3 days is considered clinically meaningful minimum change (improvement)

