Summary: This study uses a rapid and safe dose escalation to the widely accepted therapeutic range where evaluation of response will be undertaken with frequent scoring. Different maximal doses are used for children < or ≥ 15 kg, based on pharmacokinetic data. Doses are titrated to clinical effect or maximum target dose, whichever is lower. Once in the therapeutic range, doses change after 3 days if there is not an adequate reduction in symptoms. For any subject that obtains clinical benefit below maximal dose, then they will be held at that dose for the remainder of that period until such time as the scheduled wean begins. At the end of each treatment period there is a wash-out.

Starting Dose: The starting dose of gabapentin will be 5 mg/kg administered as oral liquid or via gastric or jejunal routes. On Day 1 of the study, the gabapentin will be administered once at bed-time and then increased according to the schedule shown in Table 1.

Dose Escalation: The dose will be increased every 3^{rd} - 4^{th} day in a step wise fashion of 13% - 50%, starting with the evening dose in order to accommodate sedation. The maximum dose for subjects will be as follows: < 15 kg to 60 mg/kg day and \geq 15 kg to 45 mg/kg/day. Dose titration will be to a maximum target dose (based on weight as described, < 15 kg, > 15kg) or to clinical effect, whichever is lower. The dose escalation scheme is based upon expert consensus and personal communication with [name], [name], and upon review with the BC Children's Hospital research pharmacist. \cdot , 56.

Some children with PIUO and SNI have been given gabapentin empirically by their health care provider, often without any subsequent, detailed assessment of benefit. Many times, the medication is continued because of its low side-effect profile and overall safety compared with other analgesics. If a subject is currently on gabapentin at the time of enrolment, and the parent/caregiver wants an evaluation of its effectiveness, then the subject can be enrolled in this study with the following approach:

After appropriate enrolment and consent, the subject will be weaned off of gabapentin, in a stepwise manner with 25% reductions in dose every 3rd day. Once they are no longer on the active drug, they will be randomized to active drug or placebo like all other study participants.

Gabapentin Risks and Precautions

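### Protocol Section 6.2 gives one maximum of 60 mg/kg/day for the whole treatment arm, while the Summary, Section 3.3 and the dosing tables give 45 mg/kg/day for the heavier weight group

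*Protocol*

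**What the plan says.** The maximum dose is stated in four places in the protocol.

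- **Section 1, Trial Summary (medication administration and dosing).** "The dose will be escalated as described in Section 6.2". After that pointer it continues: "The maximum dose is 60 mg/kg/day in participants < 15 kg, or 45 mg/kg/day (675 mg) in participants > 15 kg".
- **Section 3.3, Interventions (regimen text).** "Different maximal doses are used for children < or ≥ 15 kg, based on pharmacokinetic data". The dose-escalation paragraph repeats the two figures: "The maximum dose for subjects will be as follows: < 15 kg to 60 mg/kg day and", then, after a greater-than-or-equal sign, "15 kg to 45 mg/kg/day".
- **Section 3.3, dosing tables.** There is one table for children under 15 kg, in mg per kg, and another headed "Active Participants > = 15kg in mg per day".
- **Section 6.2, Trial Design Summary.** The treatment-arm dose is raised "until an effective dose or maximum dose (60mg/kg/day) is reached, whichever comes first". This sentence carries no weight condition, and nothing else in the text of Section 6.2 supplies one.

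Section 2.3 also tells the reader where the dosing table is. The section number is printed with a gap but is evidently 3.3.

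**The concern.** A maximum dose in a paediatric titration trial should read the same wherever it is stated. Here the sentence in Section 6.2 applies to everyone on active drug and agrees with the rest of the protocol only for children under 15 kg. For heavier children it matches neither the Summary, nor the text of Section 3.3, nor the peak of their table.

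The cross-reference makes this more than a loose line in an overview. The Summary names Section 6.2 as the description of escalation. A reader who goes there finds no step schedule in the text and a single unsplit ceiling.

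The ceiling is one of the two conditions that end upward titration, the other being clinical effect. Section 3.3 rests the weight split on pharmacokinetic data, names sedation as the most common adverse event and relies on the titration scheme to limit it. Those who run the trial should not have to infer which of two ceilings governs.

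**Working it through.** **1. The plan's own figure.** The Summary equates 45 mg/kg/day with 675 mg. The arithmetic is 45 x 15 = 675 mg/day, so the figure holds at a body weight of exactly 15 kg. It equals the peak of the heavier-group table: 3 x 225 = 675 mg/day on days 14 to 17.

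**2. The stated maxima side by side (mg/kg/day).**

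| Place in the protocol | Lighter group | Heavier group | How the heavier group is defined |
|---|---|---|---|
| Section 1, Summary | 60 | 45 (675 mg) | above 15 kg |
| Section 3.3, text | 60 | 45 | 15 kg and over (once written as above 15 kg) |
| Section 3.3, tables | 60 (3 x 20, days 17 to 19) | 45 (675 mg/day, days 14 to 17) | 15 kg and over |
| Section 6.2 | 60 | 60 | no split |

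The lighter group is consistent throughout. The heavier group is not: three statements say 45 and one says 60. The Summary assigns no maximum to a child of exactly 15 kg, whereas the Section 3.3 text and table heading put that child in the heavier group.

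**3. Size.** 60 / 45 = 1.33, so the Section 6.2 ceiling is a third above the other one in mg/kg terms. At 15 kg: 60 x 15 = 900 mg/day against 45 x 15 = 675 mg/day, a difference of 225 mg/day.

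**4. Where the pointers lead.** The Summary sends the reader to Section 6.2 for escalation. Section 2.3 sends the reader to Section 3.3 for the dosing table, and the day-by-day tables are there. Section 3.3 refers to its schedule as Table 1, which Section 6.1 lists among the appendix tables; the tables in Section 3.3 carry no such label in the text at hand. The Summary's pointer thus differs from that in Section 2.3 and from where the tables stand.

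**5. Does the Section 6.2 sentence alter the primary window?** In the lighter table, days 11 to 13 are at 40, days 14 to 16 at 50 and days 17 to 19 at 60 mg/kg/day. In the heavier table, days 11 to 13 are at 40, days 14 to 17 at 45 and days 18 to 19 at 30 mg/kg/day. The sentence in Section 6.2 changes none of these rows.

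**The case against.** The case for leaving this alone is that nobody would dose from Section 6.2. The sentence is one bullet in an overview, without days, steps or amounts. The Summary gives the weight split directly after its pointer, so anyone who follows the pointer has just read it. The heavier-group table has no row above 45 mg/kg/day. Caregivers dose from a daily tracker and the pharmacist's instructions. Reaching 60 mg/kg/day in a heavier child would require rows that no table contains. All of this stands, and it limits the practical effect. It does not remove the contradiction.

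Figures in and just before Section 6.2 are not shown in the text available, so what the section displays in full cannot be checked. That leaves some doubt about the cross-reference, but none about the sentence on the maximum.

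Two stronger readings are tempting. A reader might infer that the dose tested on days 11-19 is undetermined for heavier children. The documents do not show this: it would need staff to depart from the tables, and no documented dosing step uses the Section 6.2 ceiling. A reader might also set 60 mg/kg/day against the fixed 675 mg/day for a much heavier child; at an assumed 40 kg that is 2,400 against 675 mg/day. Most of that gap comes from the heavier-group table being in fixed milligrams, which is a separate question. On the mg/kg figures the comparison at 40 kg is 2,400 against 1,800 mg/day, again a ratio of 1.33.

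**Conclusion.** The protocol contradicts itself on the maximum dose for the heavier weight group. Section 6.2 gives 60 mg/kg/day without a weight split; the Summary, the Section 3.3 text and the Section 3.3 tables give 45. The discrepancy is 33%, or 900 against 675 mg/day at 15 kg. The Summary's cross-reference points to the section with the conflicting figure and not to the one with the tables. A smaller inconsistency goes with it, namely whether exactly 15 kg belongs to the heavier group.

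The conclusion rests on the plain reading of an unqualified maximum stated for the whole treatment arm, and on the text at hand without its figures. It takes no view on which ceiling is right and claims no demonstrated effect on dosing or on the primary outcome. It is worth correcting because it concerns a dose ceiling in children and is cheap to put right.

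**What to change.** Three wording changes in one amendment:

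- Reconcile the maximum in the Trial Design Summary of Section 6.2 with the Trial Summary, the Section 3.3 text and the two dosing tables. The sponsor must confirm which maximum applies to which children.
- Define the weight boundary in the same way everywhere, so that a child of exactly 15 kg falls into one stated group.
- Redirect the Trial Summary's cross-reference for dose escalation from Section 6.2 to the dosing tables in Section 3.3.

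The changes add no data collection, and reconciling these statements leaves the planned analyses as they are.
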